4. BACKGROUND INFORMATION

4.1. Background and Clinical Rationale

The normal tear film is a relatively stable, thin film composed of a superficial lipid layer and an aqueous layer intermixed with a mucous gel layer, which is partially adherent to the corneal and conjunctival surface epithelium. Dysfunction of one or more components of the tear film can lead to loss of tear film stability and symptoms of dry eye. The majority of patients with dry eye are prescribed artificial tears to alleviate symptoms and maintain a healthy ocular surface.

The purpose of this study is to evaluate the retention time of the lipid components of the new emulsion OM3 Tear eye drops via tear collection and analysis in evaporative dry eye (EDE) and non-EDE patients. Tear film evaporation rate, tear lipid profile via interferometry and tear lipid components will be evaluated before and 15 mins, 1 hour and 4 hours after the first dose, and again after 4 weeks of use of the emulsion OM3 Tear eye drops, compared to two comparators (Optive Advanced Unit Dose and Optive Unit Dose).

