5. STUDY OBJECTIVES AND CLINICAL HYPOTHESIS

5.1. *Study Objective*

The objective of this study is to measure tear film evaporation rate, tear lipid profile via interferometry and tear lipid components with the use of the emulsion OM3 Tear eye drops, compared to two comparators (Optive Advanced Unit Dose and Optive Unit Dose) in subjects with EDE and those without (non-EDE)

5.2. *Clinical Hypothesis*

Tear evaporation rate as measured with the Vapometer is better (i.e. lower) with the emulsion OM3 Tear formulation compared to at least one of the two comparators at one or more of the post eye drop instillation time-points.

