6. STUDY DESIGN

This study is a single centre, double-masked, randomized, 3-arm comparison of emulsion OM3 eye drops compared to two comparators. All study subjects will attend a Screening visit and receive REFRESH PLUS® for 2 weeks during a run-in period prior to randomization. Subjects will be randomized as to the order of allocation to use the OM3 Tear eye drop and the two comparators. For each arm of the study, assessments will be conducted prior to eye drop instillation and 15 min, 1 hour and 4 hours post-instillation. Subjects will then be dispensed with the randomized study eye drop and instructed to instill 1 to 2 drops of their assigned study product in each eye, as needed, but at least twice daily, for 4 weeks. Subjects will attend a 4 week visit assessment and then undergo a minimum 2 week wash-out period using run-in product REFRESH PLUS® before returning to complete the next arm of the study. These procedures will be repeated until the subjects have completed all 3 arms of the study.

The primary endpoint is a measurable difference in tear evaporation rate between the eye drops after initial application (15 min) and/or after 1 hour and/or 4 hours of application and/or after 4 weeks of daily use.

All proposed procedures conform to the NHMRC Statement on Human Experimentation.

Participants are considered enrolled when they have signed the informed consent form and are regarded as part of the clinical trial population.

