6.1. Methodology / Study Visits

6.1.1. Data Requirements per Visit with Visit window (\pm days)

The data requirements for each visit are shown in Table 4.

Table 4

	Visit 1	Visit 2a	Visit 2b*	Visit 2c	Visit 3a	Visit 3b*	Visit 3c	Visit 4a	Visit 4b*	Visit 4c
Timeline	Day - 14	Day 1 #1	Day 1 #1	4 weeks #1	6 weeks #2	6 weeks #2	10 weeks #2	12 weeks #3	12 weeks #3	16 weeks #3
Procedure										
Informed Consent	Y	N	N	N	N	N	N	N	N	N
Inclusion/Exclusion criteria	Y	Y	N	N	N	N	N	N	N	N
Ocular, medical history, medications, demographics	Y	N	N	N	N	N	N	N	N	N
Updated history, symptoms, problems	Y	Y	N	Y	Y	Y	Y	Y	Y	Y
Vision tests	Y	Y	Y	Y	Y	Y	Y	Y	Y	Y
Biomicroscopy (ocular health, staining)	Y	Y	N	Y	Y	N	Y	Y	N	Y
Meibomian gland assessment	Y	N	N	N	N	N	N	N	N	N
Schirmer test (eligibility)	Y	N	N	N	N	N	N	N	N	N
Instill eye drops	Y	Y	N	N	Y	N	N	Y	N	N
Tear evaporation rate	N	Y	Y	Y	Y	Y	Y	Y	Y	Y
Eye photo (ocular surface area)	Y	N	N	N	N	N	N	N	N	N
Schirmer test (tear collection)	N	Y	Y	Y	Y	Y	Y	Y	Y	Y
LipiView	N	Y	Y	Y	Y	Y	Y	Y	Y	Y
TBUT (fluorescein)	N	Y	Y	Y	Y	Y	Y	Y	Y	Y
Questionnaires (OSDI, VAS)	Y	Y	Y	Y	Y	Y	Y	Y	Y	Y

Y = Yes, required information, N = No, not required

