6.1.2. Randomisation and Masking

Prior to initiation of study treatment, each subject who provides informed consent will be assigned to a subject number that will serve as the subject identification number on all study documents. Subject numbers will be assigned in ascending order and should not be omitted or reused.

At the Screening visit (Visit 1), all eligible subjects will receive run-in product (REFRESH PLUS) for use during the 14-day run-in period. The clinical site will dispense the run-in product. At the time of randomization (Visit 2, Arm 1), eligible subjects will be randomly assigned to 1 of the 3 treatments. A randomization scheme will be prepared in advance.

Study product will be labeled with study product kit numbers. At Visit 2 (Arm 1), the specific study product kit number for each randomized subject will be dispensed by unmasked administrative study personnel and all study measurements will be conducted by the masked investigator. Unused study product will be returned at the 4 week follow-up visit and the run-in product will be dispensed to be used during the wash-out period. This procedure will be repeated until all arms of the study have been completed.

The emulsion OM3 Tear formulation and the two comparator unit dose eye drops will be provided in similar 0.4 mL unit-dose vials (comparator products will have commercial labeling).

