6.1.4. Trial Duration

This study is a randomized 3-arm comparison of emulsion OM3 eye drops compared to two comparators. Participants will attend a Screening visit (Day -14) and up to 3 scheduled visits for each eye drop. It will take participants

approximately 18 weeks to complete all 3 arms of the study.

Table 5: Visits

Visit Type:	Visit No:	Study Arm
Screening (Day -14)	1	-
Eye Drop #1: Baseline and 15 min assessment	2a	1
Eye Drop #1: 3-5 hour assessment	2b	1
Eye Drop #1: 4 week assessment	2c	1
Eye Drop #2: Baseline and 15 min assessment	3a	2
Eye Drop #2: 3-5 hour assessment	3b	2
Eye Drop #2: 4 week assessment	3c	2
Eye Drop #3: Baseline and 15 min assessment	4a	3
Eye Drop #3: 3-5 hour assessment	4b	3
Eye Drop #3: 4 week assessment and Exit	4c	3

All study participants will attend a Screening visit and receive REFRESH PLUS® for 2 weeks during a run-in period prior to randomization at Visit 2a. After the 4 week assessment, all study participants will undergo a minimum 2 week wash-out period using run-in product REFRESH PLUS® before returning to complete the next arm of the study. These procedures will be repeated until the subjects have completed all 3 arms of the study.

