13.1.3. Analysis

Participants who have commenced the study treatment will be included in the analysis dataset. Reasons and frequency distribution of participants discontinued at the Screening visit will be reported. The analysis of efficacy variables such as subjective ratings will employ only scheduled and evaluable visits. The analysis of safety variables such as adverse responses will include all visits, including all unscheduled visits.

Data will be summarised as means \pm standard deviations for variables measured on an interval scale and median \pm inter-quartile range for ordinal variables. Statistical tests will be employed to determine significant differences between between visits and $p \leq 0.05$ will be considered statistically significant. . Multiple comparisons will be adjusted using Bonferroni's correction. Commonly used tests of significance at each visit may include paired t-tests and group t-test for parametric data and Wilcoxon sign rank test and rank sum test for non-parametric data or repeated measures Analysis of Variance (ANOVA) for parametric data to determine differences between within-subject factors. Ranked variables will be analysed non-parametrically using Friedman's analysis of variance or Wilcoxon Signed Rank test to determine differences. Paired categorical variables will be compared using McNemar's test and grouped categorical variables will be analysed using Chi-Square tests. Mann Whitney U test will be used to compare tear film lipidome between the eye drops.

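### The lipidome comparison between drops uses an independent-samples test (Mann-Whitney U) on data that the crossover design makes paired

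*Combined protocol and SAP*

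**What the plan says.** **Design.** Section 6: "Subjects will be randomized as to the order of allocation to use the OM3 Tear eye drop and the two comparators". Section 6.1.2, on dispensing, return of product and wash-out: "This procedure will be repeated until all arms of the study have been completed". Section 6.1.4: "After the 4 week assessment, all study participants will undergo a minimum 2 week wash-out period" before the next arm. Despite the label of three arms, this is a three-period crossover.

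**Sampling.** Table 4 in section 6.1.1 marks the Schirmer tear-collection row as required at all nine treatment visits (2a to 4c), three under each drop.

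**Analysis.** Section 13.1.3: "Mann Whitney U test will be used to compare tear film lipidome between the eye drops". The synopsis (Statistical Considerations) has the same sentence. For ranked variables, section 13.1.3 names Friedman's "analysis of variance or Wilcoxon Signed Rank test to determine differences", and the synopsis also names a linear mixed model. Neither is assigned to the lipidome.

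**Importance.** Section 4.1: "The purpose of this study is to evaluate the retention time of the lipid components of the new emulsion OM3 Tear eye drops". The objective in section 5.1 includes "tear lipid components with the use of the emulsion OM3 Tear eye drops". The primary endpoint (6.2) is tear evaporation rate. The secondary endpoints (6.3 and synopsis) do not name the lipidome.

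**The concern.** Mann-Whitney takes its null variance from two independent samples. Here the two samples are the same participants measured under two drops. If a participant's values under two drops are positively correlated, the between-drop contrast varies less than the test supposes. The test then rejects too rarely under the null and can miss real differences. If the correlation is negative, it rejects too often. Either way the nominal 5% is not the actual level, and the main statistical benefit of a crossover, using each participant as their own control, is given up for the lipid data. What is at stake is the conclusion on whether the new emulsion changes tear lipids relative to the comparators. The evaporation-rate result is not affected.

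**Working it through.** **Inputs from the documents.** Up to 40 participants, about 20 per stratum (13.1.1); 5% significance level (13.1.2); Bonferroni correction (13.1.3). No lipidome effect size, variance or correlation is given.

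**The plan's own figure.** The only planning figures are for evaporation rate: difference 36, SD 50, 80% power, two-sided 5%. The ratio is 36/50 = 0.72. If 50 is read as the SD of paired differences, a paired t-test needs 17.2, so 18 participants. With an assumed 10% dropout, 18/0.9 = 20, the stated size per stratum. No figure for the lipidome exists to reproduce.

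**Assumptions.** One lipidome value per participant per drop at a time point; normal values (for example on the log scale); shift of 0.72 SD (borrowed from evaporation rate) or 0.5 SD; r from -0.3 to 0.7; complete data unless stated.

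**Step 1: actual type I error.** With paired normal values, the large-sample null variance of the Mann-Whitney statistic is (1 - r_s) times the value the test uses, where r_s = (6/π)·arcsin(r/2) is the rank correlation. The actual two-sided level is therefore 2·[1 - Φ(1.96/√(1 - r_s))].

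| r | r_s | 1.96/√(1 - r_s) | Level by formula | Simulated, n = 20 |
|---|---|---|---|---|
| -0.3 | -0.288 | 1.727 | 8.4% | 8.2% |
| 0 | 0 | 1.960 | 5.0% | 4.9% |
| 0.3 | 0.288 | 2.322 | 2.0% | 2.1% |
| 0.5 | 0.483 | 2.725 | 0.6% | 0.8% |
| 0.7 | 0.683 | 3.481 | 0.05% | 0.1% |

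Signed-rank stays close to 5% throughout.

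**Step 2: power, complete data, 5% level.** Simulated (at least 20,000 datasets per setting), Mann-Whitney v signed-rank:

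| r | n = 20, 0.72 SD | n = 40, 0.5 SD | n = 40, 0.72 SD |
|---|---|---|---|
| 0 | 58 v 56% | 58 v 57% | 87 v 87% |
| 0.3 | 59 v 71% | 59 v 72% | 91 v 96% |
| 0.5 | 61 v 85% | 60 v 86% | 94 v 99% |
| 0.7 | 64 v 97% | 64 v 97% | 97 v 100% |

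**Step 3: corrected level.** With three drop pairs, 0.05/3 = 1.67%. At n = 40 and 0.72 SD the figures are about 79 v 90% at r = 0.3 and 82 v 97% at r = 0.5. At n = 20 and 0.72 SD they are about 36 v 52% and 35 v 69%.

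**Step 4: missing values.** Signed-rank uses only complete pairs. If 20% of values are missing independently per drop, 0.8 × 0.8 = 64% of pairs remain. At n = 20, 0.72 SD and the 5% level, Mann-Whitney / signed-rank / mixed-model power is then about 47/36/51% at r = 0, 46/47/60% at r = 0.3 and 47/62/74% at r = 0.5. Signed-rank overtakes Mann-Whitney between r = 0.25 and 0.30.

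**The case against.** **Every driver of the size is assumed.** Correlation, effect size, distribution and missingness for the lipidome are not in the documents. This stands. The power figures are a range under assumptions, with no gain at r = 0 and a small one for a 0.72 SD shift with all 40 participants at the 5% level. The sentence names no stratum, so n = 40 is a natural reading.

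**Assay and sampling details are partly blacked out.** If samples were pooled across participants, or each drop were assayed in different people, the pairing argument would not apply as put here. This stands as a condition. Nothing visible suggests either.

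**The test might be meant for EDE against non-EDE participants, where it would be valid.** The wording does not allow this: both places say the comparison is between the drops.

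**Section 6.1.2 speaks of assignment to one of three treatments.** That describes the first period; the same section repeats the procedure until every arm is done.

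**The plan already lists paired tests.** It does, but as general options. The lipidome sentence is firm and names a different test.

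**Stronger readings to resist.** A reader might infer that the lipidome analysis will produce false positives. That needs negative correlation, which nothing in the documents suggests; under positive correlation the test is conservative. A reader might also infer that the trial's main result is compromised. It is not, because the lipidome is neither a primary nor a named secondary endpoint. Nor do the documents support a large loss of power in every setting.

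**Conclusion.** The point holds. As written, an independent-samples test is prescribed for paired data, in two places, and no other part of the plan supplies a paired lipidome analysis. The mismatch of test and design is certain if there is one value per participant per drop. The consequence depends on r: the level falls to about 2% at r = 0.3 and 1% at r = 0.5, and rises to about 8% at r = -0.3. For positive r and complete data, the power given up at r = 0.3 to 0.5 and the 5% level is about 12 to 26 percentage points for the smaller sample or the smaller shift, and about 5 points for n = 40 with a 0.72 SD shift. It should be fixed because lipid components are part of the stated purpose and objective and the correction is cheap. It does not threaten the primary conclusion.

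**What to change.** In section 13.1.3 and in the synopsis, replace the Mann-Whitney sentence with one pre-specified paired analysis, for example:

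> Tear film lipidome will be compared between the eye drops within participant, using Wilcoxon signed-rank tests on paired differences, with a linear mixed model on log values (participant random; drop and period fixed), which keeps participants with incomplete data, as a supporting analysis; Bonferroni correction applies as in 13.1.3.

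The order of the two analyses should be fixed in advance. A rule that switches to the mixed model as soon as any value is missing would in practice almost always switch: with 5% of values missing (assumed) and three drops, a fully complete time point has probability 0.95^60 = 4.6% for 20 participants and 0.95^120 = 0.2% for 40.

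**Cost.** Wording only; no new data, and both methods are already named in the plan. Signed-rank drops incomplete pairs, so it can be less powerful than Mann-Whitney when many values are missing and correlation is low (36% v 47% at r = 0 with 20% missing). This matters most at the optional 4-hour visit. The mixed model recovers those participants but relies on roughly normal log values with similar variances under each drop.

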13.2. Criteria for Termination of the Trial

The trial will be terminated upon completion of the final visit by the last active participant or unless any of the conditions of Section 7.4 are met. An active participant is one who is enrolled in the study and has not been discontinued.

13.3. Accountability of Data

Individual data points that are missing will be excluded from analysis involving only those specific variables. A participant's complete visit data will not be excluded if some of the observations are missing. Data from unscheduled visits will be used only for adverse response analysis. Inclusion of outliers in the analysis will be based on the magnitude of change in test statistic with and without the outliers. Outliers will preferably be retained unless there is significant change in test results.

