11.2. Methods

Ocular comfort will be assessed by completion of paper-based questionnaires

[REDACTED]

History (including medical and general health) will be recorded on the Participant History File at all visits.

Habitual visual acuity will be measured at each visit using standard letter charts.

A photograph of the anterior eye will be taken at the Screening visit only for participants who are eligible to continue into the randomization phase of the study. From the photograph, ocular surface area will be measured in order to calculate the absolute tear evaporation rate.

Tear evaporation rate will be measured using the Vapometer. To minimize the effect of skin evaporation, petroleum jelly (Vaseline_, <http://www.unilever.com.au/brands-in-action/detail/Vaseline/299339/>) will be applied over the upper eyelid and the surrounding areas. Three measurements will be taken for each eye under open eye and closed eye conditions. Each measurement will be recorded and the absolute evaporation rate will be calculated for each eye.

Tear lipid layer thickness will be measured using the LipiView Ocular Surface Interferometer. The participant's eye is positioned in front of an illumination source that is directed toward the tear film on the corneal surface. The camera records a 20-second video of the tear film interference and subsequently displays a value in

interferometric colour units (ICU), where 1 ICU approximates 1nm of lipid layer thickness

Slit lamp biomicroscopy will be performed at each visit. This will be used to assess the following variables and rated using the CCLRU (Appendix II) and CIBA grading scales (Appendix III).

- Bulbar conjunctival redness
- Corneal and conjunctival staining (in conjunction with fluorescein and a Wratten 12 filter)

Tear break-up time (TBUT) will be performed with the application of fluorescein and a yellow barrier filter. A stopwatch will be used to record the first occurrence of true tear break-up, not just local thinning or tear film irregularity. Three consecutive TBUTs will be performed per eye and the time in seconds for each of the three measurements will be recorded.

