13.1.1. Number of Participants

Up to 40 participants will be recruited (approx. 20 EDE and 20 non-EDE subjects). This sample size was calculated on the basis of detecting a difference in: tear evaporation rate between the eye drops of 36 gm²/h where the expected standard deviation of the measurement is 50 gm²/h, assuming an estimate of type 1 error $\alpha = 0.05$ and power of 80% for a two tailed test.

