13.1.2. Significance

A p-value less than or equal to 5% will be considered to be statistically significant.

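### Section 13.3 drops outliers when dropping them changes the test result, with neither term defined, so the 5% level is not controlled

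*Combined protocol and SAP*

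**What the plan says.** Section 13.3 (Accountability of Data) has two sentences on outliers. The criterion is "Inclusion of outliers in the analysis will be based on the magnitude of change in test statistic with and without the outliers". The direction is "Outliers will preferably be retained unless there is significant change in test results".

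Section 13.1.2 sets the level: "A p-value less than or equal to 5% will be considered to be statistically significant". Section 13.1.3 adds the only other error control: "Multiple comparisons will be adjusted using Bonferroni's correction". On data quality, section 13.1 mentions only range checks and frequency distributions.

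On the unit of data, section 11.2 says of evaporation rate: "Three measurements will be taken for each eye under open eye and closed eye conditions". TBUT is also timed three times per eye.

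**The concern.** The trigger for removing a value is its effect on the test. It is not a device fault, a recording error or a masked data review. Four things are left open:

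- what counts as an outlier;
- how large a change in the result is significant;
- whether the outlier is a single reading, an eye or a participant's value;
- whether the person deciding has seen the results by treatment.

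Nothing elsewhere in the document closes these gaps.

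At stake is the error rate for the primary endpoint. With about 20 participants per stratum and at most 40 in all, one or two values can move a t statistic across the threshold. Bonferroni does not help, because it adjusts p-values computed after the exclusion has been decided.

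**Working it through.** **Inputs from the plan.** Two-sided α = 0.05 (sections 13.1.1 and 13.1.2). About 20 participants per stratum and up to 40 in all (section 13.1.1). Each participant receives all three drops in random order (section 6), so comparisons between drops are within participant. The paired t-test is among the listed tests (section 13.1.3).

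**The plan's sample size (context only).** The standardised difference is 36/50 = 0.72. A paired t-test with "power of 80% for a two tailed test" then needs n = 18, and n = 20 gives 86.3% power. This fits about 20 per stratum only if 50 is the SD of the paired difference, which the plan does not say. The outlier point does not rest on it.

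**Assumptions.** The plan gives no outlier definition, so common ones were tried: beyond 2, 2.5 or 3 SD of the mean, or outside the 1.5×IQR or 3×IQR fences. All were applied to participant-level paired differences. A significant change was read as a change in the verdict at p ≤ 0.05.

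**What the rule does on that reading.** If both analyses agree, the choice between them does not matter. If they disagree, the outliers are dropped. The verdict is therefore always that of the analysis without outliers, and the stated preference for retention never affects a conclusion. Hence:

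rate under the rule = rate with all values kept + share of null datasets gaining significance − share losing it.

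For normal data, n = 20 and 1.5×IQR: 5.0% + 4.2% − 0.3% = 8.9%. Gains dominate because removing extreme values shrinks the SD in the denominator of t, while the ordinary t reference distribution is still used.

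**False-positive rate (%) of one nominal 5% paired t-test, true null, 200,000 simulated trials per setting**

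| n | Differences | All kept | 3 SD | 2.5 SD | 1.5×IQR | 2 SD |
|---|---|---|---|---|---|---|
| 20 | normal | 5.0 | 5.3 | 6.6 | 8.9 | 10.0 |
| 20 | t, 5 df | 4.7 | 5.4 | 6.5 | 9.4 | 8.9 |
| 20 | t, 3 df | 4.3 | 5.4 | 6.4 | 9.5 | 8.0 |
| 40 | normal | 5.1 | 5.6 | 7.0 | 7.8 | 10.5 |
| 40 | t, 5 df | 4.9 | 5.8 | 7.0 | 8.7 | 9.1 |
| 40 | t, 3 df | 4.5 | 5.8 | 6.6 | 9.1 | 8.2 |

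A separate simulation (60,000 datasets for each n and distribution, all five cut-offs, 30 cells) gave 5.0% to 5.9% for 3 SD or 3×IQR, 6.3% to 7.0% for 2.5 SD, and 7.6% to 10.1% for 1.5×IQR or 2 SD. Gains exceeded losses in all 30 cells, by at least 2.4 to 1.

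**Other readings of the rule**

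- Outliers dropped whenever t moves by more than 0.5: 5.3% to 10.4% at n = 20 and 5.6% to 9.6% at n = 40.
- Outliers dropped only when that gains significance: 5.3% to 11.3%.
- Cut-off also chosen after seeing the results: 11.4% to 12.9%.

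**With Bonferroni.** Assuming three pairwise drop comparisons, the level per test is 0.05/3 = 1.67%. The rate under the rule is 1.7% to 2.1% with 3 SD or 3×IQR, and 3.1% to 4.6% with 1.5×IQR or 2 SD.

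**Estimate.** With symmetric null data, the mean after removal stayed within about 0.002 of zero. The problem shown is the error rate, not bias in the estimated difference.

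**The case against.** **The figures measure trimming, not selection.** On the verdict reading they equal the rates from always removing the flagged values, so a fixed, masked removal rule with the same cut-off would do as badly. Using whichever analysis is significant adds at most about 1.7 points. Section 13.3 is also worded both ways: it would drop an outlier that creates significance. This is correct. It limits what the numbers can be blamed on, but it does not make the rule acceptable, because 13.3 still leads to the trimmed t-test whenever the conclusion depends on it.

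**The size comes from assumed cut-offs.** With 3 SD or 3×IQR the verdict reading adds less than one point to 5%, and nothing in the plan points to the looser cut-offs. That stands. But nothing in the plan excludes them either, and the cut-off may be chosen with results in view.

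**Only one unit was tabulated.** If single readings are removed instead (three per drop, one eye, normal data, replicate SD assumed to be 0.3 or 1.0 times the between-participant SD), the rate is 5.0% to 5.3% with 3 SD, 5.5% to 6.0% with 1.5×IQR and 6.3% to 8.2% with 2 SD. The harm is smaller on that reading, but still present with the looser cut-offs.

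**The test family may be larger.** Two comparators at four time-points (sections 5.2 and 6.2) make eight tests. With Bonferroni over eight, the family-wise error is 4.5% to 6.0% with 3 SD or 3×IQR and 7.2% to 16.1% with looser cut-offs. Again the cut-off decides.

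**Other tests and other causes.** Rank tests, ANOVA and mixed models were not simulated, and rank tests are less sensitive to extreme values. The and/or primary endpoint and the menu of tests also loosen error control. Both points are fair: the outlier rule is one contributor, but it needs its own correction.

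**Conclusion.** The rule is wrong as written and must be fixed. Whether a value counts depends on the result it produces, both operative terms are undefined, and no other section bounds the effect.

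For one paired t-test at nominal 5%, the false-positive rate on the verdict reading runs from about 5% with a strict cut-off to about 10% with a loose one, and up to 12.9% if the cut-off is chosen after seeing results. These values are illustrative. They assume participant-level differences, a symmetric null distribution and cut-offs that the plan does not supply. What is firm is that a strict and a loose cut-off both comply with section 13.3, so the plan does not secure its own 5% level. No claim is made about bias in the estimate or about the size of the effect in the tests that were not simulated.

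**What to change.** Replace the two outlier sentences in section 13.3 with:

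> All recorded values are retained in the primary analysis. A value is removed only for a documented measurement or recording error, decided from source records by staff masked to eye drop, before unmasking and without reference to test results. A sensitivity analysis excluding statistical outliers, defined before unmasking as participant-level paired differences between eye drops beyond the 3×IQR fences, is reported beside the primary result and does not replace it.

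Another numerical definition would also serve if it is fixed before unmasking. The definition should state how the two eyes are combined and that it applies separately to each drop comparison and time-point. If a mixed model or ANOVA is chosen, it should also state which observations the exclusion removes. The first two sentences hold for any of the listed tests.

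With all values kept, the simulated rate returns to 4.3% to 5.1%. The cost is a short text change and one sensitivity table, with no new data, visits or participants. Some results may look less favourable than under the current rule.
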